#### Research question and objectives

#### **Research question:**

What is the safety profile and clinical effectiveness of rapidly infused CT-P10 in patients with NHL or CLL in the real world clinical setting?

#### **Hypothesis:**

This is a descriptive study and there is no a priori hypothesis to be tested.

#### **Primary research objective:**

To describe the incidence of infusion-related reactions (IRR) associated with rapid infusion of CT-P10 in patients with NHL or CLL on day 1 or day 2 after the index event (index event defined as the first rapid infusion of CT-P10, which must have been given as part of the second or a subsequent treatment cycle).

#### Secondary research objectives:

To describe the following in patients who receive rapid infusion of CT-P10 for the treatment of NHL or CLL:

- 1. Safety profile in the 6 months post-index date (index date defined as the date of the first rapid infusion of CT-P10, which must have been given as part of the second or a subsequent treatment cycle), including incidence (and frequency per patient per month, where appropriate) of the following safety events: IRRs, grade 3 or grade 4 IRRs, any adverse event (AE), any serious adverse event (SAE), any grade 3 or grade 4 AE, AEs as the primary cause for treatment discontinuation.
- 2. Clinical effectiveness in the 6 months post-index date (to be analysed separately for NHL and CLL), including overall survival (OS), progression free survival (PFS), best response, overall (complete/partial) response rate, time to complete or partial response.
- 3. NHL / CLL treatment patterns during the observation period (from diagnosis of NHL or CLL to 6 months post-index date), including types and doses of treatment, number and duration of infusions, time on treatment and reasons for discontinuation.
- 4. Patients' demographic, clinical, and NHL/ CLL disease characteristics.

#### Study design

A European, multi-centre, retrospective non-interventional post-authorisation safety study (PASS) based on secondary use of hospital medical records. The study will involve the collection of patient-level data from hospital medical records for patients with NHL or CLL who received treatment with CT-P10 in selected centres in five European countries. Patients will be selected based on the treatment they received as part of their standard clinical care in the real world. Data will be collected retrospectively from the date of diagnosis of NHL or CLL until the index date (defined as the date of the first rapid infusion of CT-P10 [as part of the second or a subsequent treatment cycle]), to capture patients' demographic and clinical characteristics, and for a period of 6 months post-index (or until death, if sooner), to capture safety and clinical outcomes.

# Population Setting

Study sites will be specialist treatment centres or hospitals that routinely use CT-P10

for the treatment of patients with NHL or CLL, recruited from five European countries (the UK, Spain, France, Italy and the Netherlands). At least two centres will be included from each country.

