## 9.2 Setting

#### 9.2.1 Study population

The source population for this study is adult patients with NHL or CLL who received treatment with rapidly infused CT-P10 as part of their standard clinical care in five European countries.

Patients fulfilling the following criteria will be potentially eligible for inclusion in the study:

- Patients with a confirmed diagnosis of NHL (follicular lymphoma [FL] or diffuse large B-cell lymphoma [DLBCL]) or CLL.
- Patients who had received rapidly infused CT-P10 for their second or a subsequent treatment cycle; 'rapidly' defined as 90-minutes or less.
- Patients at least 18 years of age at the date of diagnosis of NHL or CLL.
- Patients (or next of kin, if appropriate locally) providing written informed consent for study data collection (if this is required according to local country regulations).

Patients fulfilling any of the following criteria will be excluded from the study:

- Patients who had received reference rituximab for any previous treatment cycles
   (i.e. prior to the index event) within the same line of treatment.
- Patients whose medical records are unavailable for review.

As only limited exclusion criteria will be applied, and patients will be included from a range of centres in five European countries, it is expected that the study population will be representative of the overall source population.

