#### 9.2.4 Study sites

Study sites will be specialist treatment centres or hospitals which routinely use CT-P10 in the treatment of patients with NHL or CLL, recruited from five European countries (the UK, Spain, France, Italy and the Netherlands). Based on the target sample size, each country will recruit approximately 60 patients. To reduce any bias potentially arising from using a single site in one country, at least two centres in each country will be included to meet the country targets. Centres will be selected based on their current practice of rapidly infusing CT-P10.

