# Endpoint to address the primary objective

# Variables required to address the primary objective

Primary objective: To describe the incidence of IRR associated with rapid infusion of CT-P10 in patients with NHL or CLL on day 1 or day 2 after the index event (index event defined as the first rapid infusion of CT-P10, which must have been given as part of the second or a subsequent treatment cycle).

Proportion of patients who experience an IRR\* on day 1 or day 2 after the index event.

- Did IRR(s) occur on day 1 or day 2 after the index event (Yes/No)?
- \* An IRR is defined as any AE from a predefined list (see Annex 3) occurring on day 1 or day 2 after an infusion of CT-P10.
- If yes, IRR description and date

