#### 9.9 Limitations of the research methods

- Patient or next of kin consent may be a requirement for this study in some of the participating countries; this may introduce selection bias, resulting in a study sample that may not be representative of the wider patient population of
- **Thterest**erpretation of data collected retrospectively will be dependent on the completeness and quality of the medical records and the reliability of the abstraction of data from the medical records.
- The primary endpoint of this study is the incidence of IRR on day 1 or day 2 after the index event. It is expected (based on scoping interviews) that IRRs occurring during or shortly after the CT-P10 infusion should be reliably documented in

patients' infusion records, however, it is possible that IRRs occurring the day after the infusion may be less well-documented. This may result in an underestimate of the overall incidence of IRR during the observation period, particularly of milder events. The IRR rate may also be underestimated as a result of the definition of a rapid infusion as 90 minutes or less, since this may result in the exclusion of cases where the initial intention was to infuse CT-P10 over 90 minutes, but the infusion was delayed or stopped due to IRRs.

- The patient records included in this study will be from physicians and study sites
  that are willing to participate. Therefore, study findings may not be generalisable
  to all patients with NHL or CLL treated with rapid infusion of CT-P10 or to all
  physicians who treat these patients in the participating countries.
- As this is a non-interventional study conducted in a routine clinical practice setting, the assessment of treatment response may not be uniform, particularly with regard to the timing of evaluations. In particular, it is likely that disease progression for the identified patients will have been monitored at less frequent intervals than would be required in a clinical trial and therefore progression events will be identified later. This may result in upwardly biased estimates of PFS. For this reason, any findings regarding the endpoints of clinical response should be considered to be 'real world estimates' which may not be directly comparable to those observed in clinical trials.
- This is a descriptive study and no adjustments to control for confounding will be carried out.

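### Selecting centres on present rapid-infusion practice risks a downward bias in the IRR proportion that section 9.9 does not name

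*Protocol*

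**What the plan says.** The target is defined by past exposure. Section 9.2.1 states: "The source population for this study is adult patients with NHL or CLL who received treatment with rapidly infused CT-P10", as part of standard care in the five countries. The same section then says that, because exclusions are few and centres varied, "it is expected that the study population will be representative of the overall source population".

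Centres are admitted on present behaviour. The abstract's setting paragraph requires only routine use of the product ("Study sites will be specialist treatment centres or hospitals that routinely use CT-P10") and does not mention rapid infusion. Section 9.2.4 repeats that requirement and adds the sentence that matters here: "Centres will be selected based on their current practice of rapidly infusing CT-P10".

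The primary endpoint in section 9.3 is the share of patients with an IRR on day 1 or day 2 after the first rapid infusion. Section 9.7.1 gives it a 95% CI and compares it by Z-test with published reference rituximab rates.

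On site selection, section 9.9 says: "The patient records included in this study will be from physicians and study sites" and continues "that are willing to participate. Therefore, study findings may not be generalisable". It attaches no direction to this. It does name two other routes to an underestimate: poorer recording of next-day reactions, and the 90-minute definition ("The IRR rate may also be underestimated as a result of the definition of a rapid infusion as 90 minutes or less").

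**The concern.** A record review needs centres that have given rapid CT-P10, not centres that still do. Whether a centre still does may depend on the reactions it saw. Section 7 explains that the slower standard schedule exists to limit IRRs, so reactions are a plausible reason for returning to it. Where that happened, the centre's patients belong to the source population but cannot enter. Section 9.2.2 takes every eligible patient at a participating centre, so the choice of centre is one of the main points where selection can act.

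If such centres exist and had more reactions than the rest, the study's IRR proportion would be too low for the population it claims to describe. Neither the confidence interval nor a larger sample would reveal this, and the understated rate would carry into the Z-test. The study is a safety study meant to inform treatment decisions, so an undisclosed error in the favourable direction matters more than one of the same size the other way.

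**Working it through.** **The passages side by side.** Source population (9.2.1): patients who received rapid CT-P10, at any time. Site criterion (9.2.4): centres that infuse it rapidly when sites are chosen. The two coincide only if no centre has stopped, or if those that stopped have the same IRR rate. The caveat in 9.9 does not cover the gap, because a centre that stopped and is willing to take part still fails the 9.2.4 criterion.

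**The plan's own precision figure.** Section 9.5 gives 6.8% to 14.0% for a 10% rate with 300 patients. An exact (Clopper-Pearson) interval for 30/300 reproduces this; Wilson gives 7.1% to 13.9% and Wald 6.6% to 13.4%. The exact interval also reproduces the 9% row, 6.0% to 12.8%, so the half-width at 9% is (12.8 - 6.0)/2 = 3.4 points.

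**Illustrative size.** The documents give neither the share of source patients at centres that stopped (s) nor the IRR rate there (q). I assume s = 5% to 20% and q = 15% to 30%. The upper value of q is the highest rate among the published rituximab studies mentioned in 9.5, not a figure for any centre that stopped. The rate at continuing centres is taken as 9%, close to the 8.84% literature mean in 9.5.

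Source rate = 9% x (1 - s) + q x s; understatement = s x (q - 9%).

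| s | q = 15% | q = 30% |
|---|---|---|
| 5% | 8.55 + 0.75 = 9.30%; 0.30 points | 8.55 + 1.50 = 10.05%; 1.05 points |
| 10% | 8.10 + 1.50 = 9.60%; 0.60 points | 8.10 + 3.00 = 11.10%; 2.10 points |
| 20% | 7.20 + 3.00 = 10.20%; 1.20 points | 7.20 + 6.00 = 13.20%; 4.20 points |

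**What it takes to matter.** To reach 3.4 points, q must be 9 + 3.4/0.20 = 26% when s = 20%, and 9 + 3.4/0.10 = 43% when s = 10%. The second is above any rate the protocol mentions.

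**The other side of zero.** If s = 0 or q = 9%, the understatement is 0. If the centres that stopped had a lower rate, say q = 5% with s = 20%, the source rate would be 7.20 + 1.00 = 8.20% and the study would overstate by 0.8 points.

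**Effect on coverage.** With 300 patients and a true rate of 10% at included centres, the nominal 95% interval covers a source rate of 11% about 93% of the time, 12% about 86%, and 14% about 45%. On a 10% base, 14% requires s = 20% and q = 30%.

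**The case against.** The strongest reply is that nothing in the protocol shows that any centre abandoned rapid CT-P10. Approval came in February 2017 and data collection starts in May or June 2018 (section 6 and the abstract differ), so there were only about 15 months in which to adopt and drop it. Section 7 also reports low IRR incidences with rapid rituximab, and use in over 70% of 20 UK centres surveyed. This stands as a reason to expect the effect to be small. It does not show that the effect is absent.

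A reader might infer that the rule can remove only unfavourable experience and so must bias the rate downward. The documents do not support that. Section 9.2.4 shuts out every centre that stopped, for whatever reason; supply, cost or staffing would be unrelated to the IRR rate. A centre could also stop after one severe event without a raised proportion. Downward is the expected direction only where reactions were the reason.

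A reader might also take the abstract's sentence as excluding centres that gave up rapid infusion. It does not: a centre that kept CT-P10 but slowed its infusions satisfies it. The restriction rests on 9.2.4.

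Two further replies stand in part. Section 9.9 already warns that findings may not extend to all patients given rapid CT-P10. That caveat covers this population, but it names a different mechanism and no direction. Present rapid use also has a practical purpose: 9.2.4 looks for about 60 patients per country, and 9.2.2 allows a second recruitment round, to which a centre that has stopped adds no newly eligible patients. That is a cost to weigh against the wider criterion.

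**Conclusion.** The point holds as a risk, not as a demonstrated bias. Section 9.2.4 selects centres on a feature that can depend on the primary outcome. The retrospective design does not require it, section 9.2.1 expects a representative sample, and section 9.9 names neither the mechanism nor its likely direction.

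The size is unknown and may be zero. The range of 0.3 to 4.2 points rests wholly on the assumed shares and rates, all of which put the excluded centres above 9%. Within that range, only the corner with about a fifth of patients at nearly three times the rate or more exceeds the 3.4-point half-width. The sample size and the confidence interval arithmetic checked here are unaffected. The change is worth making because it is cheap, removes an avoidable weakness in a safety estimate, and would show whether such centres exist.

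**What to change.** 1. In section 9.2.4, make a centre eligible if it has given CT-P10 by rapid infusion at any time, whether or not it still does. Align the routine-use wording there and in the abstract, so that it does not bring the restriction back for a centre that has since left the product.
2. At site feasibility, ask every approached centre whether rapid CT-P10 was stopped or restricted, and why. Report how many such centres were approached and how many were included.
3. Qualify the representativeness sentence in section 9.2.1.
4. In section 9.9, name whatever selection on continued rapid use remains, with its likely direction, separately from willingness to participate.

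The cost is protocol wording and one feasibility question. The downside is that centres that stopped may contribute few patients for the set-up effort, and no newly eligible ones to a second recruitment round. If feasibility finds no such centre, that answer can be reported and the concern falls away.

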#### Study population

The source population for this study is adult patients with NHL or CLL who received treatment with rapidly infused CT-P10 as part of their standard clinical care in five European countries.

Patients fulfilling the following criteria will be potentially eligible for inclusion in the study:

- Patients with a confirmed diagnosis of NHL (follicular lymphoma [FL] or diffuse large B-cell lymphoma [DLBCL]) or CLL.
- Patients who had received rapidly infused CT-P10 for their second or a subsequent treatment cycle; 'rapidly' defined as 90-minutes or less.
- Patients at least 18 years of age at the date of diagnosis of NHL or CLL.
- Patients (or next of kin, if appropriate locally) providing written informed consent for study data collection (if this is required according to local country regulations).

Patients fulfilling any of the following criteria will be excluded from the study:

- Patients who had received reference rituximab for any previous treatment cycles (i.e. prior to the index event) within the same line of treatment.
- Patients whose medical records are unavailable for review.

#### **Variables**

The exposure of interest in the present study is treatment with CT-P10, administered by rapid infusion. All study patients will be exposed by virtue of the inclusion criteria. The primary outcome is the proportion of patients who experience IRRs associated with rapidly infused CT-P10 on day 1 or day 2 after the index event.

The secondary outcomes for this study are described in detail in section 9.3; these will include the following parameters for patients with NHL or CLL treated with rapidly infused CT-P10:

- Overall safety profile in the 6 months post-index date
- Clinical effectiveness in the 6 months post-index date
- NHL/CLL treatment patterns during the observation period.
- Patients' demographic, clinical and NHL/CLL disease characteristics

#### **Data sources**

All data for the study will be sourced from patients' hospital medical records (paper and/or electronic, as applicable locally), infusion records and other local databases or electronic systems.

#### Study size

The proposed sample size for this study is 300. Given that the study is primarily descriptive, aiming to characterise the IRR rate in patients receiving rapid infusion of CT-P10, assessments of the utility of this sample size is primarily based on the precision with which rates can be estimated. The mean frequency/incidence of IRRs for rapidly infused rituximab across a range of studies was reported to be 8.84% (95% confidence interval [CI]: 7.12 to 10.81) in a meta-analysis by Polwart.

Assuming the rate of IRRs in patients receiving rapid infusion of CT-P10 are similar to those found in previous rituximab studies (rounding to 10%), we can expect the 95% CIs to be between 6.8 and 14.0% with a sample size of 300; a 95% CI width of 7.2%. If the sample size for the study was increased by 100 patients, the gain in precision would be a 95% confidence interval width of 6.2%, while for 200 patients the width would increase to 8.8%. The highest IRR rates among the studies investigated by Polwart gave an IRR rate of approximately 30%. For this IRR rate the 95% confidence interval would span between 24.9 and 35.5% for a sample of 300. Given the diminishing returns of the effect of increasing study sample size on the precision of estimates derived, a sample size of 300 patients is considered to be acceptable.

The expected sample size split for patients with NHL and CLL is based on the epidemiology of both diseases, with approximately 76,800^17 and 20,200^18 patients with NHL and CLL, respectively, being alive at the end of 2010 in the UK. Based on these prevalence estimates, and assuming a similar prevalence across Europe, it is expected that the sample will comprise approximately 240 patients with NHL and 60 with CLL who received rapid infusion CT-P10.

#### **Data analysis**

For the primary endpoint analysis, the frequency and proportion of patients receiving CT-P10 who experience IRRs on day 1 or day 2 after the index event will be presented with 95% confidence intervals (CI). The proportional Z-test will be used to compare the IRR rate observed in this study with rates previously reported for reference rituximab in the literature.

For the secondary endpoint safety analyses, rates of events per-patient-per month will be reported. The time-to-event clinical effectiveness endpoint analyses (OS, PFS, time to complete or partial response) will be displayed descriptively using Kaplan Meier plots.

For the demographic, clinical, and NHL/CLL disease characteristics endpoint analyses, the study population will be described by means of summary statistics. Appropriate tests for differences between disease groups will be employed according to the data distribution.

Summary statistics will be displayed for the treatment dose and duration on

treatment, and for the reasons for treatment discontinuation.

#### Milestones

Start of data collection: Jun 2018. End of data collection: Dec 2018.

Final report of study results: Feb 2019.

# 5. Amendments and updates

All amendments to this protocol will be documented in the table below.

Protocol deviations will be documented in a Protocol Deviation Log (maintained in a separate document).

Number	Date	Section of study protocol	Amendment or update	Reason	

## 6. Milestones

Milestone	Planned date
Registration in the EU PAS register	Apr 2018
Start of data collection	May 2018
Interim analysis (for submission to ASH 2018)	July 2018
End of data collection	Dec 2018
Publication at ASH 2018	Dec 2018
Publication at EHA 2019	Jun 2019
Final report of study results	Feb 2019

# 7. Rationale and background

In February 2017, CT-P10 became the first monoclonal antibody biosimilar version of rituximab to be approved by the European Medicines Agency (EMA). It is licensed as Truxima™ for intravenous use in adults with rheumatoid arthritis, granulomatosis with polyangiitis and microscopic polyangiitis, and specific blood cancers including non-Hodgkin's Lymphoma (NHL) and Chronic Lymphocytic Leukaemia (CLL). Clinical similarity between CT-P10 and rituximab

has been accepted by the EMA based on evidence in a population of patients with moderate to severe rheumatoid arthritis using the American College of Rheumatology-20 response and in a population of patients with follicular lymphoma (FL) using overall response rate as markers of clinical effectiveness.

The safety profile of rituximab has been documented in numerous clinical trials, with infusion-related reactions (IRRs), thought to be related to the release of cytokines, being the most commonly reported adverse reaction. The majority of these occur at the first infusion and decrease with subsequent infusions, with the peak time to onset ranging from 30 to 120 minutes. IRRs are usually mild to moderate in nature with symptoms such as fever, rash, and cardiovascular or respiratory insufficiency; more severe anaphylactic type reactions occur rarely. To minimise the risk of IRRs, the standard administration protocol for rituximab, specified in the summary of product characteristics, takes approximately three to four hours for the first infusion and two to three hours for subsequent infusions for oncology treatment. The recommended initial rate for first infusions is 50 mg/hour; after the first 30 minutes, this is gradually increased in 50 mg/hour increments every 30 minutes, to a maximum of 400 mg/hour. Patient observations are undertaken every 15 minutes. Second infusion rates start at an initial rate of 100 mg/hour, increasing at 100 mg/hour increments at 30 minute intervals, to a maximum of 400 mg/hour. This standard infusion protocol places a significant burden on the healthcare system in terms of the lengthy observation times required and impact on nursing and administration staff workloads, and may also be inconvenient for patients; consequently, many healthcare professionals now administer rituximab as a rapid infusion (over 90 minutes or less) for second or subsequent infusions in patients who did not experience serious complications with their initial infusion(s). For example, a survey conducted in 2009 of 20 major UK cancer centres found that over 70% were using rapid rituximab infusion protocols.

A number of studies have been conducted to evaluate the safety of rapid infusion of rituximab in patients with haematological malignancies and have generally shown rapid administration to be safe, with low incidences of IRRs. In addition, the safety of rapid infusion rituximab has been investigated in patients with rheumatoid arthritis, with one systematic review reporting that both the 90 minute, and a shorter 60 minute schedule, appear to be well-

tolerated. However, with the exception of a recently-published abstract reporting data from a single UK centre, there are no data available on the safety of rapid infusion of CT-P10.

This study will address this evidence gap by collecting real world data on the safety and effectiveness of rapid infusion of CT-P10 in patients with NHL and CLL in Europe. In so doing, it will provide physicians and healthcare providers with more detailed information on the safety profile of rapidly infused CT-P10, to enable them to make evidence based decisions on the most appropriate and cost-effective treatment strategy.

